- k. Tinnitus as the primary purpose for seeking cochlear implantation
- 1. Subject obtains a severe or catastrophic score on the Tinnitus Handicap Inventory (Newman, Jacobson & Spitzer, 1996).
- 3. Enrollment
 - a. This study seeks to enroll twenty (20) subjects
- B. Participants: Control group

Subjects must meet the following inclusion criteria and not exhibit any of the exclusion criteria.

- 1. Inclusion Criteria
 - a. Unilateral moderate-to-profound sensorineural hearing loss
 - i. Unaided residual hearing thresholds from 250-8000 Hz (PTA ≥70 dB HL on the implanted side)
 - ii. Normal to mild residual hearing thresholds from 250-8000 Hz in the contralateral ear ≤35 dB HL at each frequency, 250-8000 Hz
 - b. Recipient of bone-conduction device on affected side
 - i. Recipient of the Bone-Anchored Hearing Aid (BAHA)
 - a. Either the Cochlear BAHA Connect or Attract system
 - ii. At least 12 months of listening experience with the BAHA system
 - c. Greater than or equal to 18 years of age
 - d. Duration of moderate-to-profound sensorineural hearing loss less than or equal to 5 years at time of implantation with bone-conduction device (BAHA)
 - i. Either reported by the subject or documented in previous audiograms
 - e. Willingness to participate in test battery
- 2. Exclusion Criteria
 - a. Non-native English speaker

- i. Speech perception materials are presented in English
- b. Conductive hearing loss in either ear
- c. Compromised auditory nerve, including those with a history of vestibular schwannoma
- d. Inability to participate in test battery
- 3. Enrollment
 - a. This study seeks to enroll at least 10 subjects in the control group
- C. Timeline

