Appendix A graphically depicts the timeline and associated measures

The Candidacy Evaluation and Preoperative Evaluation can either occur during the same visit or two different visits.

- 1. **Candidacy Evaluation.** This interval may overlap with the Preoperative Evaluation interval.
 - a. Audiologic Evaluation
 - i. Unaided air- and bone-conduction thresholds in both ears
 - a. Air-conduction assessed with inserts
 - ii. Unaided word recognition in both ears
 - a. Measured with recorded CNC words (50-word list)
 - b. Masking provided when appropriate
 - iii. Tympanometry in both ears
 - iv. Aided word recognition in the affected ear
 - a. Measured with recorded CNC words (50-word list)
 - b. Masking applied to the contralateral ear
 - v. Completion of the Tinnitus Handicap Inventory
 - vi. Determine if potential subject meets candidacy criteria
 - b. Medical Evaluation
 - i. Determine if potential subject is healthy enough to undergo cochlear implantation
 - ii. Associated imaging studies
 - a. This is standard of care for these patient populations
 - b. May also be completed at Preoperative Evaluation
 - iii. Discussion of alternative treatment options
 - iv. Determine if potential subject meets candidacy criteria
 - c. Informed Consent
 - i. Review and discussion of consent form
 - ii. Provide time for subject to review consent form and ask questions
 - iii. Provide subject with a signed copy of the completed consent form

2. **Preoperative Evaluation**. This interval may overlap with the Candidacy Evaluation interval.

The Preoperative Evaluation will be completed within 6 months of the surgery date.

- a. Audiologic Evaluation
 - i. Obtain a case history, including but not limited to:
 - a. Onset of hearing loss
 - b. Progression to moderate-to-profound sensorineural hearing loss
 - c. Suspected etiology of hearing loss
 - ii. Unaided air- and bone-conduction thresholds in both ears
 - a. Air-conduction assessed with insert phones
- iii. Unaided word recognition with CNC words in both ears
 - a. Measured with recorded CNC words (50-word list)
 - b. Masking provided when appropriate
- iv. Tympanometry in both ears
- v. Subjects will complete the test battery detailed in section VII.D.
 - a. Two listening conditions:
 - i. unaided
 - ii. bone-conduction test device or BAHA
 - a. The bone-conduction test device will be the Cochlear BAHA Intenso on a headband

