 - b. Mapping will be completed by board-certified audiologists. Mapping procedures will be similar to conventional cochlear implant recipients.
- iv. Counseling on the external device and use

c. One-Month Post-Initial Activation

- i. Completion of test battery listed in VII.D.
- ii. Speech perception assessed with the cochlear implant on and contralateral ear masked
 - a. CNC words
- iii. Mapping of the external speech processor
- d. Three-Months Post-Initial Activation
 - i. Completion of test battery listed in VII.D.
 - ii. Speech perception assessed with the cochlear implant on and contralateral ear masked
 - a. CNC words

- iii. Mapping of the external speech processor
- e. Six-Months Post-Initial Activation
 - i. Completion of test battery listed in VII.D.
 - ii. Speech perception assessed with the cochlear implant on and contralateral ear masked
 - a. CNC words
- iii. Mapping of the external speech processor
- f. Nine-Months Post-Initial Activation
 - i. Completion of test battery listed in VII.D.
 - ii. Speech perception with the cochlear implant on and contralateral ear masked a. CNC words
- iii. Mapping of the external speech processor
- g. Twelve-Months Post-Initial Activation (study endpoint)
 - i. Completion of test battery listed in VII.D.
 - a. Additional listening condition: bone-conduction test device or BAHA
 - ii. Speech perception with the cochlear implant on and the contralateral ear masked
 - a. CNC words
- iii. Mapping of the external speech processor
- D. Test Battery

The following test battery will be completed at each assessment interval (preoperative, and 1, 3, 6, 9 and 12 months postoperatively). All assessment and mapping will be conducted at the Carolina Crossing research lab by a board-certified audiologist.

- 1. Unaided Diagnostic Assessment
 - a. Air-conduction thresholds in both ears
 - i. Air-conduction assessed with insert phones
 - ii. Assess bone-conduction thresholds if there is a PTA shift of >15 dB as compared to the previous interval
- 2. Tympanometry for each ear
- 3. Sound Field Measures

The Carolina Crossing research lab features a 180° arc with 11 speakers spaced 18° apart. This arc will be utilized during the speech perception and localization measures.

Postoperative aided sound field assessment will be completed with the subject listening with the Opus 2 speech processor.

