Subjects who utilize a hearing aid in the contralateral ear may continue to use this technology during the sound field test conditions where the contralateral ear remains open. Hearing aid output will be measured using NAL-NL1 targets.

- a. Aided thresholds with the external speech processor on will be measured using pulsed, warble tones
 - i. Frequencies assessed: 250-8000 Hz, including all inter-octaves
 - ii. Masking presented to the contralateral ear
- b. Speech Perception Measures

Recorded materials will be presented at 60 dB SPL.

- i. Speech Perception in Quiet
 - a. Listening condition
 - i. Speech 0° azimuth
 - b. Speech perception materials
 - i. CNC words
 - ii. AzBio sentences
- ii. Speech Perception in Noise
 - a. Listening conditions
 - i. Speech and noise 0° azimuth
 - ii. Speech 0° azimuth and noise to implanted side
 - iii. Speech 0° azimuth and noise to contralateral ear
 - b. Speech perception materials
 - i. AzBio sentences
 - a. If >50% at SNR+10, then SNR+5
 - b. If >50% at SNR+5, then SNR+0
 - ii. BKB-SIN sentences with adaptive SNR
- iii. Listening Conditions
 - a. Cochlear implant speech processor off
 - i. Contralateral ear only
 - b. Cochlear implant speech processor on
 - i. Cochlear implant + contralateral ear
- c. Localization
 - i. The stimulus is a 200-ms speech-shaped noise, presented at 70-dB SPL from one of the 11 speakers (evenly spaced -180 to 180 degrees), selected at random
 - ii. The intensity level for each stimulus presentation will be randomly varied (10 dB around 70 dB SPL)
 - iii. The listener will be facing the center speaker during stimulus presentation. The task is to identify the source of the noise. No feedback is provided.
 - iv. Listening Conditions

- a. Cochlear implant speech processor off
 - i. Contralateral ear only
- b. Cochlear implant speech processor on
 - i. Cochlear implant + contralateral ear
- 4. Subjective questionnaires
 - a. Speech, Spatial and Qualities of Hearing Scale (SSQ), Gatehouse & Noble (2004)
 - b. Abbreviated Profile of Hearing Aid Benefit (APHAB), Cox & Alexander (1995)
 - c. Tinnitus Handicap Inventory, Newman, Jacobson & Spitzer (1996)
- E. Aural Rehabilitation

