 - 1. Subjects will participate in two aural rehabilitation sessions with a board-certified speech-language pathologist. One session will be after the initial activation of the external speech processor. This will occur either on the same day as the initial activation or within the first 2 weeks of listening experience. The second session will be scheduled in conjunction with the 1-month post-initial activation interval.

VIII. Proposed Claims

- A. Demonstrate the effectiveness of cochlear implantation in SSD subjects
 - 1. Demonstrate an improvement in speech perception abilities, localization, and/or subjective benefit in an aided (cochlear implant on) versus an unaided (cochlear implant off) condition
- B. Cochlear implantation provides similar or superior speech perception, localization, and/or quality of life as compared to that found with bone-conduction devices
 - 1. Comparison with control group performance
 - 2. Comparison within subject when listening with bone-conduction test device

IX. Statistical Analysis

- A. Descriptive summaries will be provided for the following: subject demographics, and frequency of major and minor complications/adverse events.
- B. A single-subject design will be utilized, where each subject serves as his or her own control, for analysis of objective and subjective results. A single-subject design was chosen in order to accommodate the heterogeneity that is well known to characterize auditory prosthesis research. Repeated-measures ANOVA will be calculated with a p-value of ≤ 0.05 for statistical significance. Statistical analysis will be conducted with SPSS software.
 - 1. Comparison of aided speech perception performance on word and sentence materials in the post-initial activation intervals to evaluate trends over time

- a. Comparison of the difference between the aided and unaided conditions at each follow-up interval
- 2. Comparison of localization abilities in the post-initial activation intervals
 - a. Comparison of the difference between the aided and unaided conditions for each follow-up interval
 - b. Compute the overall rms error, random error, constant error, and adjusted constant error, as described by Grantham et al (2007)
- 3. Comparison of subjective report scores in the post-initial activation intervals

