- C. The incidence of interference between ears will be assessed by comparing the speech perception performance in the 0° azimuth conditions for the contralateral ear only versus cochlear implant + contralateral ear conditions for each subject, as well as the individual's subjective report.

A sample size for the cochlear implant recipient cohort of 20 subjects was selected due to known variability in conventional cochlear implant recipient outcomes and to allow for possible dropouts (approximately 20%). A comparable study, Hansen, Gantz & Dunn (2013) evaluated 29 cochlear implant subjects with SSD, which included etiologies of sudden sensorineural hearing loss, Meniere's disease, and vestibular schwannoma. Authors reported a high degree of variability in their sample. This project will not enroll all of the etiologies included in the Hansen, Gantz & Dunn (2013) analysis (such as, Meniere's Disease with intractable vertigo or history of vestibular schwannoma), therefore a smaller sample size was selected. The inclusion/exclusion criteria associated with this study, as compared to the heterogeneity of the Hansen, Gantz, & Dunn (2013) subject sample, will allow for more generalized comments about subjective and objective outcomes of cochlear implantation in cases of SSD.

If needed, statistical consultation will be sought from the North Carolina Translational and Clinical Sciences Institute (TraCS) or UNC Odum Institute.

X. Endpoints

- A. Safety endpoint
 - 1. The primary safety endpoint is the evaluation of Adverse Events. All Adverse Events will be reported to the UNC IRB. If the UNC IRB or study investigators deem an Adverse Event unacceptable, then this would result in termination of the study.
- B. Primary effectiveness endpoint
 - 1. The primary effectiveness endpoint is the comparison of speech perception, localization abilities and/or subjective report when the cochlear implant is on versus off.
- XI. Risk Analysis

A. Potential risks

The following are risks associated with the MED-EL Concert implant, which is also included in the device description:

- 1. Loss of residual hearing
- 2. Increased vertigo
- 3. Delay of healing of the scar
- 4. Impairment of the sense of taste
- 5. Potential for swallowing difficulties
- 6. Numbness
- 7. Increased tinnitus
- 8. Stimulation of the facial nerve
- 9. Temporary pain and uncomfortable sounds during stimulation

The following are potential risks the subject may experience related to the study procedure:

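### Increased tinnitus is a listed device risk, but no per-subject change from the preoperative Tinnitus Handicap Inventory is analysed and no rule links a rise in the score to an adverse event

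*Combined protocol and SAP*

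**What the plan says.** All references are to the combined protocol and SAP.

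- **Risk.** Section XI.A, item 7 of the device risks: "Increased tinnitus".
- **Entry.** The candidacy visit (VII.C.1) includes "Completion of the Tinnitus Handicap Inventory". The exclusion criteria for implant subjects (VII.A.2) rule out a candidate if: "Subject obtains a severe or catastrophic score on the Tinnitus Handicap Inventory".
- **Follow-up.** The THI is item 4.c of the test battery in VII.D, which is introduced with: "The following test battery will be completed at each assessment interval (preoperative, and 1, 3, 6, 9 and 12 months postoperatively". Appendix A shows the same times for the questionnaires. None is scheduled at the 1-2 week follow-up or at activation.
- **Safety analysis.** Section IX.A: "Descriptive summaries will be provided for the following: subject demographics, and frequency of major and minor complications/adverse events". The THI is not named. The primary safety endpoint (X.A) is the evaluation of adverse events.
- **Questionnaire analysis.** IX.B.3 compares subjective scores across the post-activation intervals, under the repeated-measures ANOVA of IX.B. The preoperative score is not mentioned. Subjective report is part of the effectiveness endpoint (X.B).
- **Adverse events.** XIII.A.1 classes every XI.A risk as an anticipated event. Section XIV.A has events tracked individually and recorded when they occur. Neither section mentions the THI.

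**The concern.** The trial collects a direct, repeated measure of a harm that it lists, with a preoperative value for each subject, and then does not use that measure to describe the harm. The safety summary depends on what is recorded as an adverse event. The questionnaire analysis begins after activation, so it does not explicitly include the change across surgery, which is where a tinnitus effect of implantation would first appear.

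At stake is the completeness of the safety result. A subject's score could rise clearly after surgery and stay up, with the rise on file, and yet appear in no planned table unless someone also recorded an event. Subjects in the two worst grades are excluded at entry, so a later score in those grades is a deterioration since candidacy. The plan already uses that boundary but does not tabulate who crosses it.

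**Working it through.** The plan gives no figure for tinnitus, so there is none to reproduce. The only stated inputs are 20 implant subjects (VII.A.3) and about 20% dropout (IX), which implies 20 × 0.80 = 16 completers. The figure of 16 is derived, not stated.

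**1. What IX.B.3 can detect.** Let P be a subject's preoperative THI and S1, S3, S6, S9, S12 the scores after activation. Suppose the score rises by d by month 1 and stays there, so every S equals P + d.

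- Between post-activation visits, for example S12 − S1 = (P + d) − (P + d) = 0, whatever d is.
- From the preoperative score, S12 − P = d.

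The first contrast is the one named in IX.B.3. The second shows the worsening and is not named. Worsening that develops after month 1 would enter IX.B.3, but only within a group comparison.

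**2. What IX.A can detect.** Recorded tinnitus events are counted through XIII.A.1. No size of THI change is defined as an event, so the count can differ from the scores.

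**3. Would adding the preoperative score to the ANOVA be enough?** This needs assumed scores, as the documents have none. It tests a possible amendment, not the written plan.

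- 20 subjects, 17 improving by 15 points and 3 worsening by 25: mean = (17 × (−15) + 3 × 25)/20 = −9.0. Sum of squares = 17 × 36 + 3 × 1156 = 4080. SD = √(4080/19) = 14.65. t = −9.0/(14.65/√20) = −2.75, p about 0.013.
- 16 subjects, 14 improving by 15 and 2 worsening by 25: mean = (−210 + 50)/16 = −10. Sum of squares = 14 × 25 + 2 × 1225 = 2800. SD = √(2800/15) = 13.66. t = −10/(13.66/√16) = −2.93, p about 0.01.
- Simulated paired t-tests (20,000 runs, two-sided 0.05) with assumed changes of −20 or +20 points and SD 10, in 16 subjects: significant improvement in 98.6% of runs with 2 worse, 80.9% with 3 and 38.2% with 4.

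A mean change from the preoperative score can therefore look favourable while a few subjects are worse, so the useful summary is a count by subject.

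**4. What a count would deliver.** Exact (Clopper-Pearson) 95% intervals:

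| Worsened / assessed | Observed | 95% interval |
|---|---|---|
| 0/16 | 0% | 0 to 20.6% |
| 2/16 | 12.5% | 1.6 to 38.3% |
| 3/16 | 18.8% | 4.0 to 45.6% |
| 0/20 | 0% | 0 to 16.8% |
| 3/20 | 15% | 3.2 to 37.9% |

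For zero events the upper limit is 1 − 0.025^(1/n); with n = 16 this is 20.6%. The chance of seeing at least one worsened subject among 16 is 1 − (1 − p)^16: 56.0%, 81.5% and 97.2% at assumed true rates of 5%, 10% and 20%.

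**The case against.** The strongest reply is that the adverse event route already covers this. Increased tinnitus is an anticipated event by definition. Events are recorded as they occur, followed to resolution, reported to the IRB and listed for the principal investigator's review. An otologist sees subjects at 6 and 12 months (XI.B.6), and IX.A then counts events directly. This stands as far as it goes. A reader might infer that tinnitus harm is hidden from the safety result, or reaches it only if a subject volunteers it. The documents support neither. What they lack is a link between the score and the event record.

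A reader might also infer that worsened subjects are concealed inside a favourable average change. The plan states no average change from the preoperative score, so that is not the planned analysis. It calls the design single-subject, with own-control comparisons, and does not say how the THI will be summarised. An analyst might include the preoperative score on the strength of that wording, but IX.B.3 does not ask for it, and the named test is still a group ANOVA. Section IX.C shows that the plan can specify otherwise: for another listed risk, interference between the ears, it assesses incidence subject by subject.

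It is also fair to say that a count in 20 subjects is imprecise and that some score changes are ordinary fluctuation. Both points limit what the table can claim; neither is a reason to leave it out.

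**Conclusion.** The point holds as a gap in the safety reporting and is a cheap improvement. No planned analysis shows each subject's THI change from before surgery, and no rule turns a THI rise into an adverse event. Worsening that appears by month 1 and persists would therefore contribute nothing to IX.B.3 and could be absent from IX.A.

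Its size cannot be given from the documents. The scenarios with assumed scores show only that a group mean can miss individual worsening; they do not predict this trial. The precision of the proposed count is known: with 16 to 20 subjects, no worsening observed would still leave an upper limit of 20.6% to 16.8%.

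A reader might go further and treat any THI rise as harm caused by the implant. The documents do not support that. The within-subject comparison has no concurrent control for tinnitus, and the preoperative evaluation may take place up to 6 months before surgery, so part of a change could predate it.

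**What to change.** Add to Section IX.A a descriptive table of the THI for implant subjects, giving:

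- each subject's change from the preoperative score at 1, 3, 6, 9 and 12 months;
- the number worsening by at least an amount that the sponsor specifies before the data are examined;
- the number newly in the severe or catastrophic grade already used in VII.A.2, judged against the preoperative score;
- for each count, an exact 95% interval based on the subjects assessed at that visit, with that denominator shown;
- a cross-check of worsened subjects against recorded tinnitus adverse events, with discrepancies listed.

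Label the results as observed worsening, not as an effect of the implant.

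The cost is one table from data already collected, with no new visit, test or subject. The drawbacks are that some ordinary score fluctuation will be counted as worsening, more so over five visits, and that the reported tinnitus result may look less favourable.

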- B. Subjects can withdraw from the study at any time and for any reason by notifying the Primary Investigator. If the investigator identifies the need to withdraw a subject from the study for any reason, this will be discussed in person during a scheduled evaluation. Subjects may also be withdrawn if residual hearing changes in the contralateral (better hearing ear) to a moderate hearing loss of worse. In either scenario, the subject will continue to receive care irrespective of their participation in the study.

C. Investigative Team

- 1. The Principal Investigator will review completed Consent Forms and Case Report Forms, including determining candidacy.
- 2. The Principal Investigator will ensure that study site Standard Operating Procedures are followed by the study team.
- 3. Responsibilities for all study team members will be recorded in a Study Delegation Log. Not all team members will be responsible for all activities.
- 4. Communications between the Principal Investigator and study team will be maintained in the regulatory binder.
- 5. Source data will be maintained with completed Case Report Forms (such as, speech perception score sheets) when available.

XV. Confidentiality

- A. Subjects will be assigned a specific, anonymous subject number that will be associated with his or her data. Database entry will be by subject number only. All personal identifiers will be kept in a separate, secure data file that will be password protected and not associated with the study data. Only investigators will have access to the subject numbers.
- B. Subject specific binders will be maintained in a locked cabinet in the Carolina Crossing research lab. Individual data collection sheets will be coded with the subject number and placed in the subject specific binder at each interval. For analysis, the data will not included identifiable information.

- C. Data will not be shared outside the investigative team except during reporting of anonymous results.
- D. After the closure of the study, subject data will be retained for seven years. At that time, paper data will be shredded and destroyed in a HIPAA compliant manner. Electronic data will be destroyed following UNC policy.
- E. A description of the clinical trial will be available on http://ClinicalTrials.gov. This web site will not include information that can identify research subjects.

XVI. References

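### Repeated-measures ANOVA over five visits keeps only subjects with every visit (about 16 of 20 at the planned dropout); a mixed model on all observed on/off pairs would better protect against selective dropout

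*Combined protocol and SAP*

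**What the plan says.** Section IX.B names one inferential method, to be run in SPSS: "Repeated-measures ANOVA will be calculated with a p-value of ≤ 0.05 for statistical significance". It has two uses that matter here. Item B.1 is a trend across visits: "Comparison of aided speech perception performance on word and sentence materials in the post-initial activation intervals to evaluate trends over time". Item B.1.a is a contrast within each visit: "Comparison of the difference between the aided and unaided conditions at each follow-up interval". Items B.2 and B.3 do the same for localization and compare questionnaire scores across visits.

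Section VII.D sets the schedule: "The following test battery will be completed at each assessment interval (preoperative, and 1, 3, 6, 9 and 12 months postoperatively"). That gives five post-activation visits. Section X.B.1 defines the main outcome: "The primary effectiveness endpoint is the comparison of speech perception, localization abilities and/or subjective report when the cochlear implant is on versus off".

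The plan expects incomplete follow-up. The sample-size paragraph of section IX chose 20 implant recipients partly "to allow for possible dropouts (approximately 20"%). Section XIV.B adds: "Subjects can withdraw from the study at any time and for any reason". It also adds: "Subjects may also be withdrawn if residual hearing changes in the contralateral (better hearing ear) to a moderate hearing loss of worse".

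The plan states no analysis set, no rule for missed visits or withdrawals, and no covariance structure.

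**The concern.** In its standard form, repeated-measures ANOVA across five visits drops any subject who lacks one of them. The plan budgets for about 16 completers. It does not say how the earlier visits of the other 4 are used, or what happens when a remaining subject misses a visit.

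Two things are at stake. The first is precision of the across-visit trend. The second is bias. If leaving depends on scores already observed, an analysis of completers, or of those present at month 12, is unprotected. The earlier scores that could correct it have been collected but are not used.

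Section XIV.B gives one route by which this could happen. It allows withdrawal when the better ear declines, and by section VII.D the better ear alone is the implant-off condition. Leaving can therefore depend on a measured part of the on-off difference.

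**Working it through.** **Inputs from the documents.** N = 20 (VII.A.3); dropout about 20% (IX); 5 post-activation visits (VI.B); significance level 0.05 (IX.B). The documents give no effect size, SD, correlation between visits or power, so N = 20 cannot be reproduced from a power formula. Only the dropout arithmetic can be checked.

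**Complete rows.** 20 × (1 − 0.20) = 16, and 16 / 0.80 = 20. If each remaining subject also misses a visit with probability m (assumed), the expected number is 16 × (1 − m)^5:
- m = 2%: 16 × 0.98^5 = 14.5
- m = 5%: 16 × 0.95^5 = 12.4

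At month 12 alone with m = 5%, 16 × 0.95 = 15.2 subjects are present.

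**On/off pairs per measure.** Planned: 20 × 5 = 100. Complete rows: 16 × 5 = 80. All observed data: 84, 88, 92 or 96 if all 4 leave after month 1, 3, 6 or 9; 80 + 1 + 2 + 3 + 4 = 90 if one leaves after each. If all 4 leave before month 1, the count is 80 and nothing is gained.

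**Power at month 12 under random dropout.** Assume a benefit of 0.5 SD. For those present, SE = 1/√16 = 0.25 SD. The noncentrality is 0.5/0.25 = 2.0 on 15 df, and power is 46.5%. With all observed pairs the SE is about 0.24, the noncentrality is 0.5/0.24 = 2.08 on about 18 df, and power is about 50%.

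**Simulation (all settings assumed).** n = 20, five visits, mean on-minus-off difference 0.5, month-12 SD 1. There are three correlation patterns: constant 0.7; AR(1) with 0.8 between adjacent visits; and variance growing over time. The mixed model is REML with heterogeneous Toeplitz covariance and Satterthwaite df. Change means month 12 minus month 1. Strong selection is a log-odds of leaving of 1.6 per SD of low month-3 benefit (21% leave); weak selection is 0.6 per SD. Each cell gives the simpler analysis v the mixed model, in SD units except for coverage.

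| Loss of data | Quantity | Constant | AR(1) | Growing variance |
|---|---|---|---|---|
| Random dropout only | 12-month SE, those present | 0.253 v 0.239 | 0.249 v 0.241 | 0.250 v 0.240 |
| Random dropout only | Change SE, complete rows | 0.187 v 0.184 | 0.265 v 0.257 | 0.215 v 0.212 |
| Random dropout plus 5% missed visits | Change SE, complete rows | 0.216 v 0.191 | 0.304 v 0.263 | 0.247 v 0.218 |
| Low month-3 benefit, strong | 12-month bias, those present | +0.173 v 0.000 | +0.125 v −0.003 | +0.151 v +0.012 |
| Low month-3 benefit, strong | 95% CI coverage, those present | 90% v 95% | 93% v 95% | 92% v 94% |
| Low month-3 benefit, weak | 12-month bias, those present | +0.08 v −0.01 | +0.05 v −0.01 | not run |
| Unobserved month-12 benefit | 12-month bias, those present | +0.24 v +0.10 | +0.25 v +0.13 | not run |

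If high month-3 benefit drives leaving, the sign reverses: −0.18 v −0.01 (constant pattern).

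**Choice of covariance.** Under strong selection, a subject effect alone gives a 95% CI for the change that covers 95%, 85% and 90% in the three patterns. Heterogeneous AR(1) leaves a 12-month bias of +0.07, 0.00 and +0.06. Homogeneous Toeplitz leaves 0.00, 0.00 and +0.03, with 12-month coverage of 95%, 95% and 92%.

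**The case against.** The strongest reply is that the primary comparison is barely affected. A reader might infer that the ANOVA removes 4 subjects from the on-off test. The documents do not support that. Items B.1.a and B.2.a compare the conditions at each interval, such a test can use everyone present, and 16 is the number the plan budgets for. Nor does the plan prescribe deletion of incomplete subjects; that follows from the standard method and the plan's silence. Section III calls this a feasibility study, and the precision gain under random dropout is small. All of this stands.

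A reader might also infer that the results will be biased, or that many visits will be missed. The documents show neither. Withdrawal for better-ear decline is optional and its frequency is not given. The simulation selects on month-3 benefit, which is not that same route, and its strength is assumed. Fatigue, listed in XI.A, is a risk of the test session and not evidence of missed visits. VII.A requires subjects to be able to travel and comply. Dropouts may also leave between consent and month 1, where no method helps.

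What remains is that the plan expects incomplete histories, collects the data that could correct for selection on observed scores, and names a method that in its standard form does not use them.

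**Conclusion.** The point holds with limits and is worth a change, though it does not undermine the study. The loss of complete rows falls on the across-visit trend: 16 of 20 at the planned dropout, fewer if visits are missed. Under random dropout alone a mixed model adds roughly 4 points of power at month 12 (46% to 50% at an assumed 0.5 SD benefit). It adds nothing for subjects who leave before month 1.

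The main reason to act is protection against bias when leaving depends on observed scores. The 12-month bias among those present is about 0.12 to 0.17 SD under strong assumed selection and 0.05 to 0.08 SD under weak, and close to zero with all observed data. Its direction depends on who leaves. If leaving depends on unobserved benefit, the 12-month bias is reduced only in part. If loss is unrelated to outcome, there is no bias to remove. The simulated sizes rest on the assumed effect, correlations and selection, none of which the documents supply.

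**What to change.** In IX.B, replace the ANOVA by a REML linear mixed model (SPSS MIXED) of the within-visit on-minus-off difference:

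- Interval as a categorical fixed effect, with Satterthwaite df.
- A prespecified within-subject covariance that allows falling correlation and unequal variances, for example heterogeneous Toeplitz. Name homogeneous Toeplitz as the fallback if it does not converge, noting that its coverage can fall to about 92% when variances grow.
- All observed pairs from every implanted subject, including those before withdrawal. A visit with only one of the two scores is lost to this model (if 2.5% of single scores are missing, 1 − 0.975² = 4.9% of pairs).
- Measures with one score per visit (questionnaires, aided-score trends) modelled directly.
- For AzBio in noise, only differences with on and off at the same SNR. In VII.D the SNR tested depends on the score, so an SNR covariate cannot repair a difference taken at unequal levels.

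Report the 12-month on-off difference with its 95% CI, and a completer analysis. Add a sensitivity analysis that shifts the missing 12-month differences in both directions: with 20% missing, a shift of 0.5 SD moves the mean by 0.2 × 0.5 = 0.10 SD, and 1 SD moves it by 0.20 SD. State whether data from subjects withdrawn for better-ear decline are projected to month 12.

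The cost is a few sentences, with the same software and data and no extra visits. The downsides are somewhat more modelling work, up to nine covariance parameters for 20 subjects, and little gain if dropout is random.
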